### 3.2.5. Biomarker endpoints

- Biomarkers such as PD-L1 expression and tumor infiltrating CD8+ T lymphocytes in baseline tumor tissue.

**Table 3. Biomarker Definition and Determination**

Parameter	Definition	Method of Determination
PD-L1 expression	The percent of counted cells scored as PD-L1+ and qualitative assessment of PD-L1 staining on tumor and inflammatory cells as defined by cell morphology in regions of interest	Pathologist, assisted by image analysis
Tumor infiltrating CD8+ lymphocytes	The percent of counted cells that are scored as CD8+	Pathologist, assisted by image analysis

CCI [REDACTED]

- CCI [REDACTED]  
[REDACTED]  
[REDACTED]  
[REDACTED]  
[REDACTED]

- CCI [REDACTED]

### 3.4. Baseline Variables

#### 3.4.1. Study drug, study treatment and baseline definitions

In this study ‘**study drug**’ refers to avelumab, utomilumab, PF-04518600, PD 0360324 or CMP-001 and ‘**study treatment**’ (or ‘**treatment group**’) refers to one of the following.

Assignment to cohorts A1, A2 or A3, assignment to cohorts A9 or A10, and assignment to cohorts F1, F2 or F3 will be done via randomization. Assignment to all other cohorts is not randomized as described in Section 2.2.

#### Combination A

- Cohort A1 (Phase 1b/Phase 2 NSCLC): avelumab 10 mg/kg IV Q2W in combination with 500 mg utomilumab IV Q4W
- Cohort A2 (Phase 1b/Phase 2 NSCLC): avelumab 10 mg/kg IV Q2W in combination with 100 mg utomilumab IV Q4W
- Cohort A3 (Phase 1b/Phase 2 NSCLC): avelumab 10 mg/kg IV Q2W in combination with 20 mg utomilumab IV Q4W
- Cohort A4 (Phase 2 Melanoma): avelumab 10 mg/kg IV Q2W in combination with 100 mg utomilumab IV Q4W
- Cohort A5 (Phase 2 SCCHN): avelumab 10 mg/kg IV Q2W in combination with 100 mg utomilumab IV Q4W
- Cohort A6 (Phase 2 TNBC): avelumab 10 mg/kg IV Q2W in combination with 100 mg utomilumab IV Q4W
- Cohort A7 (Phase 2 SCLC): avelumab 10 mg/kg IV Q2W in combination with 100 mg utomilumab IV Q4W
- Cohort A8 (Phase 2 1L NSCLC): avelumab 10 mg/kg IV Q2W in combination with 100 mg utomilumab IV Q4W
- Cohort A9 (Phase 2 1L NSCLC): utomilumab 100 mg IV Q4W followed by utomilumab 100 mg IV Q4W in combination with avelumab 10 mg/kg IV Q2W
- Cohort A10 (Phase 2 1L NSCLC): avelumab 10 mg/kg IV Q2W followed by utomilumab 100 mg IV Q4W in combination with avelumab 10 mg/kg IV Q2W

For Cohorts A4 through A10, the projected utomilumab dose to be used is 100 mg which may be modified based upon emerging safety data for utomilumab from randomized dose cohorts of Combination A.

### **Combination B**

- Cohort B11 (Phase1b): avelumab 10 mg/kg IV Q2W in combination with 0.1 mg/kg PF-04518600 IV Q2W
- Cohort B12 (Phase1b): avelumab 10 mg/kg IV Q2W in combination with 0.3 mg/kg PF-04518600 IV Q2W
- Cohort B13 (Phase1b): avelumab 10 mg/kg IV Q2W in combination with 1 mg/kg PF-04518600 IV Q2W
- Cohort B14 (Phase1b): avelumab 10 mg/kg IV Q2W in combination with 3 mg/kg PF-04518600 IV Q2W
- Cohort B21 (Phase 2 NSCLC): avelumab 10 mg/kg IV Q2W in combination with PF-04518600 dose selected at the end of Phase 1b
- Cohort B22 (Phase 2 Melanoma): avelumab 10 mg/kg IV Q2W in combination with PF-04518600 dose selected at the end of Phase 1b (no patients will be enrolled)
- Cohort B23 (Phase 2 SCCHN): avelumab 10 mg/kg IV Q2W in combination with PF-04518600 dose selected at the end of Phase 1b

### **Combination C**

- Cohort C11 (Phase1b): avelumab 10 mg/kg IV Q2W in combination with 50 mg PD 0360324 IV Q2W
- Cohort C12 (Phase1b): avelumab 10 mg/kg IV Q2W in combination with 100 mg PD 0360324 IV Q2W
- Cohort C13 (Phase1b): avelumab 10 mg/kg IV Q2W in combination with 150 mg PD 0360324 IV Q2W
- Cohort C21 (Phase 2 tumor type to be decided among ovarian cancer, SCCHN, NSCLC, gastric cancer): avelumab 10 mg/kg IV Q2W in combination with PD 0360324 dose selected based on Phase 1b (no patients will be enrolled)
- Cohort C22 (Phase 2 tumor type to be decided among ovarian cancer, SCCHN, NSCLC, gastric cancer): avelumab 10 mg/kg IV Q2W in combination with PD 0360324 dose selected based on Phase 1b (no patients will be enrolled)

### **Combination D**

- Cohort D11 (Phase1b): avelumab 10 mg/kg IV Q2W in combination with 20 mg utomilumab IV Q4W and 0.1 mg/kg PF-04518600 IV Q2W
- Cohort D12 (Phase1b): avelumab 10 mg/kg IV Q2W in combination with 50 mg utomilumab IV Q4W and 0.1 mg/kg PF-04518600 IV Q2W

- Cohort D21 (Phase1b): avelumab 10 mg/kg IV Q2W in combination with 20 mg utomilumab IV Q4W and 0.3 mg/kg PF-04518600 IV Q2W
- Cohort D22 (Phase1b): avelumab 10 mg/kg IV Q2W in combination with 50 mg utomilumab IV Q4W and 0.3 mg/kg PF-04518600 IV Q2W
- Cohort D31 (Phase1b): avelumab 10 mg/kg IV Q2W in combination with 20 mg utomilumab IV Q4W and 1 mg/kg PF-04518600 IV Q2W
- Cohort D32 (Phase1b): avelumab 10 mg/kg IV Q2W in combination with 50 mg utomilumab IV Q4W and 1 mg/kg PF-04518600 IV Q2W
- Cohort D-1 (Phase 2 tumor type to be decided among NSCLC, melanoma, SCCHN, or bladder cancer): avelumab 10 mg/kg IV Q2W in combination with utomilumab and PF-04518600 doses selected based on Phase 1b
- Cohort D-2 (Phase 2 tumor type to be decided among NSCLC, melanoma, SCCHN, or bladder cancer): avelumab 10 mg/kg IV Q2W in combination with utomilumab and PF-04518600 doses selected based on Phase 1b

#### **Combination F**

- Cohort F1 (Phase 1b/Phase 2 SCCHN): avelumab 10 mg/kg IV Q2W in combination with 10 mg CMP-001
- Cohort F2 (phase 1b/ Phase 2 SCCHN): avelumab 10 mg/kg IV Q2W in combination with 10 mg CMP-001 and 100 mg utomilumab IV Q4W
- Cohort F3 (Phase 1b/ Phase 2 SCCHN): avelumab 10 mg/kg IV Q2W in combination with 10 mg CMP-001 and 0.3 mg/kg PF-04518600 IV Q2W

CMP-001 will be administered initially as 2 weekly subcutaneous (SC) doses followed by intra tumoral (IT) dosing at weekly intervals for 5 additional doses. After the first 7 doses, CMP-001 will be administered IT every 2 weeks (Q2W) (all cohorts).

#### **Start and end dates of study treatment:**

The date/time of first dose of study treatment in a combination group is the earliest date/time of the first non-zero dose date/time for the study drugs in the combination.

The date/time of last dose of study treatment in a combination group is the latest date/time of the last non-zero dose date/time for the study drugs in the combination.

#### **Definition of baseline:**

##### Definition of baseline for efficacy analyses in randomized cohorts

The last measurement prior to the ‘start date’ will serve as the baseline measurement for efficacy analyses. If such a value is missing, the last measurement prior to the first dose of study treatment will be used as the baseline measurement except for analyses of tumor assessments data where the baseline assessment would be considered as missing.

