## 2. INTRODUCTION

This SAP provides the detailed methodology for summary and statistical analyses of the data collected in study B9991004. This document may modify the plans outlined in the protocol; however, any major modifications of the primary endpoint definition or its analysis will also be reflected in a protocol amendment.

Statistical analyses will be performed using cleaned eCRF data as well as non-CRF data (ie, biopsy data from the central laboratory and pharmacokinetic (PK) data).

The primary analysis will occur after the last subject last visit (LSLV) has been achieved across all tumor types and combinations.

Additional analyses of the data may be performed for publication or regulatory reporting purposes.

Throughout this document ‘start date’ refers to date of randomization for randomized cohorts and first dose of study treatment for non-randomized cohorts.

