### Definition of baseline for efficacy analyses in non-randomized cohorts and for safety analyses

The last available assessment prior to the start of study treatment is defined as ‘baseline’ value or ‘baseline’ assessment for safety and efficacy (for non-randomized cohorts) analyses. If an assessment is planned to be performed prior to the first dose of study treatment in the protocol and the assessment is performed on the same day as the first dose of study treatment, it will be assumed that it was performed prior to study treatment administration, if assessment time point is not collected or is missing. If assessment time points are collected, the observed time point will be used to determine pre-dose on study day 1 for baseline calculation. Unscheduled assessments will be used in the determination of baseline. However, if time is missing, an unscheduled assessment on study day 1 will be considered to have been obtained after study treatment administration.

Patients who start treatment and discontinue from the study on the same day may have two different sets of data collected on study day 1 (one during study and one in the End of Treatment (EOT) visit). Data reported at the EOT visit are not eligible for baseline selection.

If a scheduled pre-dose measurement actually occurred post-dose, then the corresponding measurement will be treated and analyzed similar to an unscheduled post-dose measurement.

Baseline for RR and QT/QTc interval assessments will be derived from the visit where both RR and QT are not missing. Triplicate ECGs are collected in the study and the baseline for each ECG measurement is the average of the pre-dose replicate measurements on the baseline day. Unscheduled assessments will not be included in the calculation of the average. QTcB and QTcF will be derived based on RR and QT. The average of the replicate measurements will be determined after the derivation of the individual parameter at each time point.

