### **5.2.10. Adequate baseline tumor assessment**

Adequate baseline is defined using the following criteria:

- All baseline assessments must be within 28 days prior to and including ‘start date’.
- All documented lesions must have non-missing assessments (ie, non-missing measurements for target lesions and non-missing lesions assessment status at baseline for non-target lesions).

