In addition, the frequency (number and percentage) of patients with a confirmed BOR of CR, PR, SD, non-CR/non-PD (applicable only to patients with non-measurable disease at baseline), PD, and NE will be tabulated. Patients with confirmed BOR of NE will be summarized by reason for having NE status. The following reasons will be used:

- No baseline assessment
- No post-baseline assessments due to death
- No post-baseline assessments due to other reasons
- All post-baseline assessments have overall response NE
- New anti-cancer therapy started before first post-baseline assessment
- SD of insufficient duration (<6 weeks after the 'start date' without further evaluable tumor assessments)
- PD too late (>12 weeks after the 'start date')

Special and rare cases where BOR is NE due to both SD of insufficient duration and late PD will be classified as 'SD of early' (ie, SD of insufficient duration).

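### In the randomized cohorts, a tumor scan dated on the day of randomization is an adequate baseline under SAP 5.2.10 but a missing baseline under SAP 3.4.1

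*SAP*

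**What the plan says.** SAP Section 2 fixes the anchor date: the start date "refers to date of randomization for randomized cohorts and first dose of study treatment for non-randomized cohorts". Section 3.4.1 names the cohorts assigned by randomization: "Assignment to cohorts A1, A2 or A3, assignment to cohorts A9 or A10, and assignment to cohorts F1, F2 or F3". For these eight cohorts the start date is therefore the randomization date.

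Section 3.4.1 then defines the efficacy baseline in randomized cohorts: "The last measurement prior to the ‘start date’ will serve as the baseline measurement for efficacy analyses". If there is none, the last value before first dose may be used, "except for analyses of tumor assessments data where the baseline assessment would be considered as missing".

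Section 5.2.10 defines an adequate baseline tumor assessment with a different boundary: "All baseline assessments must be within 28 days prior to and including" the start date.

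For non-randomized cohorts and for safety, Section 3.4.1 has a same-day convention. When a planned pre-dose assessment falls on the day of first dose, "it will be assumed that it was performed prior to study treatment administration, if assessment time point is not collected or is missing". The immunogenicity baseline has a similar convention. The randomized-cohort efficacy baseline has none.

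Section 6.1.2.1 lists "No baseline assessment" among the reasons for a best overall response (BOR) of NE.

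**The concern.** Two definitions of the same object disagree about one calendar day, and the SAP does not say which governs. Two programmers could follow the text faithfully and derive different baselines from the same scan.

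The scan in question is a valid pre-treatment image. Losing it would have nothing to do with treatment, and any effect on the objective response rate (ORR) could only be downward. The cohorts include A1-A3, where a formal exact test is decided by a count of responders out of 28.

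**Working it through.** **Step 1: the two rules side by side.** Take a randomized patient with a single baseline scan and complete lesion data.

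| Date of the scan | 3.4.1, randomized cohorts | 5.2.10 |
|---|---|---|
| 1 to 28 days before randomization | baseline | adequate |
| Day of randomization | missing | adequate |
| After randomization, before first dose | missing | not adequate |

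Only the middle row conflicts. Section 5.3.3.3 dates an evaluation spread over several days by its earliest scan. If that also applies at baseline, the conflict is limited to patients whose baseline imaging has no scan date before the day of randomization.

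**Step 2: where the baseline is used.**
- Percent change and waterfall plot (6.2.2.1): the formula divides by the baseline sum of target lesions. With no baseline there is no value, so the patient drops out. This follows directly from 3.4.1.
- BOR and ORR (6.1.2.1): confirmed CR and PR are built from the responses reported at each time point, with no baseline condition. NE takes whatever is left, and the missing-baseline reason is then one of its labels. A reported, confirmed PR is lost only if that reason is programmed to override it. If it is, the patient stays in the ORR denominator as a non-responder.
- PFS (6.2.2.5, Tables 11 and 12): censoring at the start date depends on an adequate baseline, the term defined in 5.2.10. A same-day scan meets its timing condition.

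**Step 3: the plan's own figures for A1-A3.** Inputs from 5.1.1 and 5.1.2: n = 28, null ORR 15%, alternative 35%, one-sided alpha 0.05, reject at 8 or more responders.
- P(X ≥ 8 | 28, 0.15) = 0.0486, below 0.05.
- P(X ≥ 7 | 28, 0.15) = 0.115, so 8 is the correct boundary.
- P(X ≥ 8 | 28, 0.35) = 0.818, as claimed (at least 80%).

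The stated design reproduces, and the conflict makes no stated sample size, alpha or power wrong.

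**Step 4: what one lost responder would do, if the override were programmed.**
- 28-patient cohort: 1/28 = 3.6 points. 8/28 = 28.6% (exact 90% CI 15.1 to 45.7) rejects; 7/28 = 25.0% (12.4 to 41.9) does not.
- Chance of exactly 8 responders at a true ORR of 35%: C(28,8) × 0.35^8 × 0.65^20 = 0.127.
- 20-patient cohort: 1/20 = 5 points, for example 5/20 = 25% (10.4 to 45.6) against 4/20 = 20% (7.1 to 40.1), as in Tables 4 and 6.

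**Step 5: power in A1-A3 under the same condition.** With m of the 28 patients forced to non-response, power is P(X ≥ 8 | 28 − m, 0.35):

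| m | 0 | 1 | 2 | 3 |
|---|---|---|---|---|
| Power | 0.818 | 0.782 | 0.740 | 0.694 |

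With an assumed share q of patients affected, power is P(X ≥ 8 | 28, 0.35(1 − q)):

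| q | 0% | 2% | 5% | 10% | 20% |
|---|---|---|---|---|---|
| Power | 0.818 | 0.797 | 0.762 | 0.698 | 0.545 |

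The SAP gives no value for q. The range is an assumption, not an estimate.

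**The case against.** The best defence is that this is a loose phrase: a reader may take a measurement prior to randomization to include the same day, and 5.2.10 shows what was meant. That may well be the intent. But elsewhere in 3.4.1 the SAP writes out a same-day convention when it wants one, and here it also states that the tumor baseline is otherwise missing. Nor does 5.2.10 clearly rescue the scan, because it tests baseline assessments and 3.4.1 decides what counts as one.

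The objection is stronger on consequences. Four larger claims are tempting, and the SAP does not support them:
- A reader might infer that responders automatically become non-responders. The BOR rules contain no baseline condition for CR or PR, so this needs a programming step that the SAP neither requires nor rules out.
- A reader might infer that PFS is censored on the first day for same-day scans. The PFS rule uses adequacy, which such a scan passes on timing. Even with an inadequate baseline, death within 16 weeks counts as an event.
- A reader might think a scan between randomization and first dose is wrongly discarded. Sections 3.4.1 and 5.2.10 both exclude it, and 3.4.1 does so as an explicit exception. Keeping the tumor baseline no later than time zero is a defensible choice.
- A reader might add up planned enrollment (3 × 28 + 2 × 20 + 3 × 20 = 184) as the number affected. Only patients scanned on the randomization day are in conflict, and Section 2.2.1 says no further enrollment is planned in A9 and A10.

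The comparison with non-randomized cohorts is also limited. Their anchor is first dose, and their same-day convention is conditional: a recorded time governs, and an unscheduled same-day assessment without a time counts as post-dose.

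**Conclusion.** The contradiction is real and confined to one day: in A1-A3, A9-A10 and F1-F3, a scan dated on the randomization day is adequate under 5.2.10 and missing under 3.4.1. The certain effect of applying 3.4.1 literally is the loss of those patients from percent change and the waterfall plot.

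An effect on the primary ORR is possible but conditional. It requires at least one responder whose only baseline scan is dated that day, and a program that lets a missing baseline override reported CR or PR. If both hold, the cost is 3.6 points per responder at n = 28 and 5 points at n = 20. Among the affected cohorts only A1-A3 have a formal test; A9-A10 use estimation, and Phase 2 of Combination F has no decision rule. With the number of same-day scans unknown, no overall effect can be stated. The wording should be corrected because one patient can decide an A1-A3 test and the correction is cheap.

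**What to change.** 1. In 3.4.1, for tumor assessments in randomized cohorts, define baseline as the last measurement on or before the start date and before first dose. This matches the boundary in 5.2.10 and keeps a post-dose scan out when randomization and first dose share a date.
2. In 6.1.2.1, state that reported CR or PR is not overridden for a patient whose baseline scan meets 5.2.10.

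The cost is a few sentences of SAP wording and a matching check of the derivation programs. No new data are needed, and sample size, alpha and the decision rules stay as they are. The change should be made before response results by cohort are examined, so that the choice of boundary cannot depend on them.

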### Definition of baseline for immunogenicity analyses

The last available assessment prior to the start of treatment with avelumab is defined as ‘baseline’ result or ‘baseline’ assessment. If an assessment is planned to be performed prior to the first dose of avelumab in the protocol and the assessment is performed on the same day as the first dose of avelumab, it will be assumed that it was performed prior to avelumab administration, if assessment time point is not collected or is missing.

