will evaluate utomilumab single-agent administration, one month prior to initiation of combination treatment on Cycle 2 Day 1 (28 days after start of the single-agent treatment). Cohort A10 will evaluate avelumab single-agent administration, one month prior to initiation of combination treatment on Cycle 2 Day 1 (28 days after start of the single-agent treatment). Patients will be randomized 1:1 to Cohorts A9 and A10.

Originally, approximately 253 patients with solid tumors were planned to be enrolled in Combination A across all cohorts. Enrollment of patients into Cohorts A1 to A6 and A8 were completed as planned. In Cohort A7, 10 SCLC patients were enrolled. However, the level of clinical activity observed in Cohort A7 does not support further clinical development and further enrollment in this cohort is not planned. In addition, due to recent improvements in the standard of care for 1L NSCLC patients, the level of clinical activity observed in Cohort A10 does not support further development. Given that Cohort A9 and A10 use 1:1 randomization for enrollment, further enrollment in Cohort A9 alone would not conform with the study design. Therefore, further enrollment in Cohorts A7, A9, and A10 is not planned.

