### 3.2.3. Immunogenicity endpoints

- Anti-drug antibody (ADA) levels.

ADA titers for avelumab and utomilumab (Combination A) or for avelumab and PF-04518600 (Combination B) or for avelumab and PD 0360324 (Combination C) or for avelumab, utomilumab and PF-04518600 (Combination D) or for Avelumab and CMP-001 and utomilumab or PF-04518600 (Combination F).

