#### **4.3.4. Immunogenicity analysis sets**

The immunogenicity analysis sets will be per study drug in a combination. The analyses sets are subsets of the safety analysis set and will include patients who have at least one ADA sample collected for each study drug in the combination.

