## 6.2.6. Endpoints for immunogenicity data of avelumab and other study drugs

### Combinations A and F

The following analyses of immunogenicity data will be based on the Immunogenicity analysis set by treatment group using the data from the combined Phases 1b and 2 (Cohorts A1, A2, A3 and Cohorts F1, F2, F3) and the data from Phase 2 (Cohorts A4, A5, A6, A7, A8, A9, A10).

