**Table 14. Patients Characterized Based on Anti-Drug Antibody Results (ADA Status)**

Category	Definition	Patients at Risk (Denominator for Incidence)
ADA never-positive	No positive ADA results at any time point; ADA-negative patients (titer < cutpoint)	Number of patients with at least one valid ADA result at any time point
ADA ever-positive	At least one positive ADA result at any time point; ADA-positive patients (titer ≥ cutpoint)	Number of patients with at least one valid ADA result at any time point
Baseline ADA positive	A positive ADA result at baseline	Number of patients with valid baseline ADA result
Treatment-boosted ADA	A positive ADA result at baseline and the titer ≥ 8×baseline titer at least once after treatment with avelumab	Number of patients with valid baseline ADA results and at least one valid post-baseline ADA result
Treatment-induced ADA	Patient is ADA-negative at baseline and has at least one positive post-baseline ADA result; or if patient does not have a baseline sample, the patient has at least one positive past-baseline ADA result	Number of patients with at least one valid post-baseline ADA result and without positive baseline ADA result (including missing, NR)
Transient ADA response	If patients with treatment-induced ADA have (a single positive ADA result or duration between first and last positive result <16 weeks) and ADA result at the last assessment is not positive.	Number of patients with at least one valid post-baseline ADA result and without positive baseline ADA result (including missing, NR)
Persistent ADA response	If patients with treatment-induced ADA have duration between first and last positive ADA result ≥16 weeks or a positive ADA result at the last assessment	Number of patients with at least one valid post-baseline ADA result and without positive baseline ADA result (including missing, NR)

ADA: anti-drug antibody, NR = not reportable.

The number and percentage of patients in each ADA category will be summarized.

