#### **6.2.6.1. Time to and Duration of ADA response**

The ADA analyses described below will include patients with treatment-induced ADA.

Time (weeks) to ADA response is defined as:

$$(\text{Date of first positive ADA result} - \text{date of first dose of avelumab} + 1)/7.$$

Time to ADA response will be summarized using simple descriptive statistics (mean, SD, median, min, max, Q1, Q3).

Duration (weeks) of ADA response is defined as:

$$(\text{Date of last positive ADA result} - \text{date of first positive ADA result} + 1)/7.$$

Duration of ADA response will be censored if:

- the last ADA assessment is positive AND patient is ongoing treatment with avelumab, or
- the last ADA assessment is positive AND patient discontinued treatment with avelumab.

Kaplan-Meier estimates (product-limit estimates) will be presented together with a summary of associated statistics including the median ADA response time with 2-sided 95% CIs. ADA response rates at different timepoints will be estimated with corresponding 2-sided 95% CIs. The CIs for the median will be calculated according to Brookmeyer and Crowley (1982) and the CIs for the survival function estimates will be derived using the log-log transformation according to Kalbfleisch and Prentice (2002) (conftype=loglog default option in SAS Proc LIFETEST) with back transformation to a CI on the untransformed scale. The estimate of the standard error will be computed using Greenwood's formula.

Duration of ADA response will be displayed graphically and analyzed using Kaplan-Meier methodology. If the number of patients with ADA response is small, the Kaplan-Meier method may not provide reliable estimates. In this case, only descriptive statistics or listings will be provided

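### ADA baseline, boosting and time to ADA are tied to avelumab for every drug, so utomilumab ADA is misclassified or mistimed in sequenced cohorts A9 and A10

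*SAP*

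**What the plan says.** SAP Section 3.4.1 has one definition of baseline for immunogenicity: "The last available assessment prior to the start of treatment with avelumab is defined as" baseline. For a planned pre-dose sample taken on the day of the first avelumab dose, "it will be assumed that it was performed prior to avelumab administration, if assessment time point is not collected or is missing".

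Two other rules use the same anchor. In Table 14, treatment-boosted ADA requires the titer rise to occur "at least once after treatment with avelumab". In Section 6.2.6.1, time to ADA response is counted from the "date of first dose of avelumab".

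The scope is wider than avelumab. Section 3.2.3 lists ADA titers against both avelumab and utomilumab for Combination A. Section 6.2.6 is titled "Endpoints for immunogenicity data of avelumab and other study drugs" and includes A9 and A10 among the treatment groups. Section 4.3.4 states: "The immunogenicity analysis sets will be per study drug in a combination". The SAP gives no drug-specific ADA baseline or time origin.

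Section 2.2.1 staggers the two drugs. Cohort A9 "will evaluate utomilumab single-agent administration, one month prior to initiation of combination treatment on Cycle 2 Day 1", which is 28 days after the single-agent start. A10 has the same layout with avelumab given first.

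**The concern.** A baseline for antibodies against a drug should precede exposure to that drug, and time to onset should run from that exposure. Where all drugs in a combination start on the same day, the first avelumab dose serves for all of them. In A9 and A10 it does not serve for utomilumab.

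In A9 the utomilumab baseline may be taken after 28 days of utomilumab exposure. In A10 samples taken before any utomilumab count as post-baseline. At stake are the utomilumab ADA categories that depend on baseline, the time-to-ADA summary, and one of the two ADA groupings used for the PK comparison in Section 6.2.6.3.

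**Working it through.** **Inputs.** The dosing sequence and the 28-day interval come from SAP Section 2.2.1, the baseline rule from Section 3.4.1, the categories and denominators from Table 14, the time-to-ADA formula and its population (treatment-induced only) from Section 6.2.6.1, and the PK groupings from Section 6.2.6.3.

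**Stagger.** With Cycle 1 Day 1 as day 1 and Cycle 2 Day 1 as day 29, the interval is 29 − 1 = 28 days. This matches the SAP's own figure, and 28/7 = 4.0 weeks.

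**Time to utomilumab ADA.** Let P be the day of the first positive result, A the first avelumab day and U the first utomilumab day.

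- SAP formula: (P − A + 1)/7
- On utomilumab's own clock: (P − U + 1)/7
- Difference, SAP minus own clock: (U − A)/7

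A9: (1 − 29)/7 = −4.0 weeks. A10: (29 − 1)/7 = +4.0 weeks. Same-day start: 0.

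| First positive | A9, SAP | A9, own clock | A10, SAP | A10, own clock |
|---|---|---|---|---|
| Day 43 | 2.14 | 6.14 | 6.14 | 2.14 |
| Day 57 | 4.14 | 8.14 | 8.14 | 4.14 |
| Day 85 | 8.14 | 12.14 | 12.14 | 8.14 |

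(Weeks. For example, A9 on day 57: (57 − 29 + 1)/7 = 4.14 against (57 − 1 + 1)/7 = 8.14.)

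The A9 value can be negative. A patient positive on day 15, negative at the last pre-avelumab sample and positive again later is treatment-induced under Table 14. The formula, read literally, gives (15 − 29 + 1)/7 = −1.86 weeks.

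**Classification in A9.** Take a patient who is negative before utomilumab, converts in cycle 1 and is still positive at the last sample before avelumab.

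- The SAP labels this patient baseline ADA positive.
- Table 14 then removes the patient from both numerator and denominator of the treatment-induced, transient and persistent rates.
- The patient leaves the time-to-ADA and duration analyses, which take treatment-induced patients only.
- In the PK grouping that sets treatment-induced patients against never-positive or baseline-positive patients, the patient moves into the comparator group.

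Removing k such patients changes a treatment-induced rate a/n to (a − k)/(n − k), which is never larger than a/n. As an illustration with assumed counts: 20 patients, of whom 6 are truly treatment-induced (3 transient and 3 persistent), and the 3 persistent ones converted in cycle 1.

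- Treatment-induced: 6/20 = 30.0% becomes 3/17 = 17.6%
- Persistent: 3/20 = 15.0% becomes 0/17 = 0%
- Transient: 3/20 = 15.0% becomes 3/17 = 17.6%

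The boosted rate can also move either way. A cycle-1 converter whose titer later reaches 8 times the mislabelled baseline is counted as boosted. A truly baseline-positive patient whose reference titer has already risen under utomilumab must clear a higher threshold and may be missed.

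**Classification in A10.** The pre-avelumab sample is also a valid pre-utomilumab sample, so the error is conditional. It needs a negative or missing pre-avelumab result followed by a positive result before the first utomilumab dose. That patient is counted as treatment-induced without having received utomilumab.

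**Quantities with no avelumab date.** Ever-positive and never-positive status use any time point. ADA duration is last minus first positive date. Relative PK day is PK nominal day minus first-positive nominal day. For a given patient none of these changes, although the avelumab-anchored baseline still decides who enters the duration and before/after PK analyses.

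**The case against.** The strongest defence is that the consequences are limited. ADA is a descriptive secondary endpoint with no test or decision rule. Only two cohorts are affected; each was planned at 20 patients, and further enrollment in both is no longer planned. This stands, and it lowers the priority. It does not make the rules right for utomilumab.

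One might also say the text was written with avelumab ADA in mind. In that case the SAP has no baseline or time origin for the other drugs, whose ADA it plans to analyse, so the same sections still need correction.

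Several stronger readings are tempting, but the SAP does not support them:

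- That every A9 and A10 patient is affected. Never-positive patients are not, time to ADA covers only treatment-induced patients, and the A10 misclassification is conditional.
- That all baseline-dependent rates in A9 are too low. Boosted and transient rates can rise. Even the treatment-induced rate can gain a patient: one positive before utomilumab, negative at the last pre-avelumab sample and positive later.
- That the before/after-ADA PK timeline is shifted. Only membership of the treatment-induced group can change.
- That a planned A9-versus-A10 comparison is biased by 8 weeks. The two 4-week shifts do add to that, but the SAP summarizes ADA by treatment group and specifies no such contrast.
- That the censoring rule for ADA duration is wrong because it names avelumab. Its two conditions, ongoing and discontinued, together cover every patient whose last assessment is positive.

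**Conclusion.** The point holds for utomilumab ADA in A9 and A10. As written, the rules label A9 patients who convert in cycle 1 and remain positive at the last pre-avelumab sample as baseline positive, so the treatment-induced rate is generally understated. In A10 they allow a treatment-induced label before any utomilumab. Among patients counted as treatment-induced, time to utomilumab ADA is 4 weeks too short in A9 and 4 weeks too long in A10.

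The 4-week figure assumes dosing on the planned 28-day schedule. The A9 misclassification assumes that a utomilumab ADA sample falls between the first utomilumab dose and the first avelumab dose. The sampling schedule is in the protocol, which is not at hand, and the final numbers in A9 and A10 are not stated, so the count of affected patients cannot be given.

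This should be fixed but is not critical: the endpoint is descriptive and secondary, and the two cohorts closed early.

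**What to change.** In SAP Section 3.4.1, define ADA baseline separately for each drug as the last assessment before the first dose of the study drug whose ADA is being analysed, and reword the same-day rule to match. In Table 14 (treatment-boosted) and in the time-to-ADA formula of Section 6.2.6.1, replace avelumab with the respective study drug. The other Table 14 categories then follow from the corrected baseline. The duration-censoring conditions can stay as they are.

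The cost is SAP wording and one reference date per drug in the analysis data set. No new samples are needed. Results for avelumab ADA and for cohorts whose drugs start on the same day do not change.
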